8.10 Safety Visit **(all subjects)**

Change #37, Section 8.10, Safety Visit, bullet point 14

- Laboratory assessments for safety (to be performed only if abnormal at the EDV)
 - Hematology
 - Biochemistry (including hepatic monitoring of ALT, AST, ALP, total bilirubin, and GGT)
 - Urinalysis (for subjects ≥ 4 years of age)
 - Serum pregnancy test (if applicable)

Has been changed to:

- Laboratory assessments for safety (to be performed only if abnormal at the EDV)
 - Hematology
 - Biochemistry (including hepatic monitoring of ALT, AST, ALP, total bilirubin, and GGT)
 - Urinalysis (for subjects ≥ 4 years of age)
 - Serum pregnancy test (see Section 9.5.1)

Change #38, Section 8.11, Final Visit, header

The original text:

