Section 9.2.3.2 (Section 9.5.2.2 of Amendment 4)	Subjects receiving phenytoin as a concomitant AED during the study will have blood samples collected at the ScrV (directly enrolled subjects only), FEV, YEV, FV, and at the EDV in the case of early discontinuation to monitor phenytoin plasma concentrations. Blood samples will only be collected at the SV if the plasma levels of phenytoin are abnormal at the EDV.	Subjects receiving phenytoin as a concomitant AED during the study will have blood samples collected at the visits designated in Table 5-1, Table 5-2, and Table 5-3 to monitor phenytoin plasma concentrations.	Remove information provided in Section 5.2 to decrease redundancy.
Section 9.3 (Section 9.6 of Amendment 4)	Not applicable.	Other safety measurements will be performed at the visits indicated in Table 5-1, Table 5-2, and Table 5-3.	Provide navigational text for reader.

Section Impacted	Key components of previous text	Key components of amended text	Rationale
Section 9.3.1 (Section 9.6.1 of Amendment 4)	A standard 12-lead ECG will be performed at the ScrV, TV(s), and EV (directly enrolled subjects only), YEV, FV, and at the EDV in the case of early discontinuation. An ECG will be performed at the SV only if the ECG results at the EDV are abnormal. At the EV, for LTFU subjects, ECG data will be obtained from the final visit of the previous pediatric BRV study and should not be recorded in the eCRF for N01266.	A standard 12-lead ECG will be performed.	Remove information provided in Section 5.2 to decrease redundancy.
Section 9.3.2 (Section 9.6.2 of Amendment 4)	Vital signs, including measurements of blood pressure, supine or sitting pulse rate, and body temperature, will be performed after 5 minutes of rest at the ScrV, TV(s), and EV (directly enrolled subjects only), MEV, FEV, YEV, FV, and at the EDV, DTV, and the SV in the case of early discontinuation. For LTFU subjects, at the EV, vital sign data will be obtained from the final visit of the previous pediatric BRV study and should not be recorded in the eCRF for N01266.	Vital signs, including measurements of blood pressure, supine or sitting pulse rate, and body temperature, will be performed after 5 minutes of rest.	Remove information provided in Section 5.2 to decrease redundancy.

Section Impacted	Key components of previous text	Key components of amended text	Rationale

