^f At the SV, ECGs, laboratory assessments for safety, and determination of phenytoin plasma concentration will be performed only if abnormal at the EDV.

Amendment 4 Table 5-1: Schedule of all study assessments for LTFU subjects and assessments subsequent to the final TV for directly enrolled subjects

Period	Evaluation							Down-Titration	Safety (Drug-free)		
	Entry Visit	Minimal Evaluation Visit	Full Evaluation Visit	Yearly Evaluation Visit/Final Visit	Unscheduled Visit	Early Discontinuation Visit	Down-Titration Visit				
Visit											
(EV)	(MEV)	(FEV)	(YEV/FV ^b)	(UV)	(EDV)	(DTV) ^c					
Subjects	LTFU ^a	DE	All								
Assessment											

^a EEG (for LTFU subjects only)

- For subjects ≥ 2 years of age on the day of the study visit and with typical absence seizures: every 3 months during the first 6 months (starting at V4), and then yearly thereafter: an EEG of at least 1 hour of recording including hyperventilation and intermittent photic stimulation must be performed for efficacy assessment. For subjects prematurely discontinuing from the study, an EEG of at least 1 hour of recording should also be performed at the EDV.
- For subjects ≥ 1 month to < 2 years of age on the day of the study visit: every 3 months during the first 6 months (starting at V4), then yearly thereafter: an EEG of at least 24 hours of recording including sleeping and awakening periods must be performed for efficacy assessment. For subjects prematurely discontinuing from the study, an EEG of at least 24 hours of recording should also be performed at the EDV.

^b No DRC or study drug will be dispensed at the FV.^c The assessment of seizure types will be done at 6-monthly intervals (at the FEV and the YEV) for subjects < 2 years of age.

^j For LTFU subjects, any ongoing medications (including AEDs and non-AEDs) at the time the subject completed the previous pediatric BRV study should not be recorded in the eCRF for N01266, unless there is a change regarding the administration of the medication. In this event, the start date corresponding to the date of change in administration should be recorded in the eCRF.

^k For LTFU subjects, any ongoing AEs at the time the subject completed the previous pediatric BRV study should not be recorded on the eCRF for N01266, unless there is a change in intensity or seriousness. In this event, the AE should be recorded in the eCRF for N01266, with the onset date corresponding to the date of change in condition.

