Section 5.1	For all subjects enrolled in N01266, the maximum BRV dose is 5.0mg/kg/day (2.5mg/kg bid), not to exceed a dose of 200mg/day for subjects with body weight >40kg.	For all subjects enrolled in N01266, the maximum BRV dose is 5.0mg/kg/day (2.5mg/kg bid), not to exceed a dose of 200mg/day.	Removal of unnecessary text for clarification
	Following the EDV, subjects will have their BRV dose reduced by a maximum of half the dose every week for a maximum of 4 weeks until a dose of 1mg/kg/day (50mg/day for subjects with body weights >50kg) is reached.	Following the EDV, or following the FV for subjects who complete the study but do not continue BRV treatment, subjects will have their BRV dose reduced by a maximum of half the dose every week for a maximum of 4 weeks until a dose of 1mg/kg/day (50mg/day for subjects with body weights >50kg) is reached.	To add down-titration information for subjects who do not continue BRV treatment after completing the study
Section 5.1.1	Subject participation will extend from study entry for at least 3 years until approval of BRV has been obtained for pediatric subjects in their age range, until a managed access program is established as allowed per country-specific requirements in addition to legal and regulatory guidelines, or until the investigational product development in the related age range of the pediatric population is stopped by the Sponsor, whichever comes first.	Subject participation will extend from study entry for at least 3 years until approval of BRV has been obtained for pediatric subjects in their age range, until a managed access program is established as allowed per country-specific requirements in addition to legal and regulatory guidelines, until subjects transition to another BRV study, or until the investigational product development in the related age range of the pediatric population is stopped by the Sponsor, whichever comes first.	To allow subjects to transition to another BRV study
Table 5-2	^g No DRC or study drug will be dispensed at the FV.	^g No DRC or study drug will typically be dispensed at the FV. However, for subjects who complete the study but do not continue BRV treatment, study drug for down-titration will be dispensed.	To add down-titration information for subjects who do not continue BRV treatment after completing the study

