		
safety assessment may need to be conducted, in a format that allows the Investigator to receive and review these results and include as source documentation.
 
Deviations to data collection including inability to perform some assessments such as EEG, ECG or blood collection for safety laboratory assessments and PK, or alternative methods of assessment such as phone calls should be recorded in the source documentation and notated as “not done” in the electronic case report form (eCRF).
 
In cases where subjects cannot return to the study site, and it will not be possible to dispense a new DRC, subjects will be instructed to continue recording of seizures in a manner that is mutually agreed with the Investigator (eg, hand-written notes, taking notes on a smart device). Any recording of seizures in a manner outside of the study DRC must be carefully documented in the source medical records (copies or printouts of these recordings will be brought to and retained at site).
	
Section 7.2.2	The maximum BRV dose will be 5.0mg/kg/day (2.5mg/kg bid), not to exceed a dose of 200mg/day for subjects with body weight >40kg.	The maximum BRV dose will be 5.0mg/kg/day (2.5mg/kg bid), not to exceed a dose of 200mg/day.	Removal of unnecessary text for clarification
Section 7.2.3	All subjects who prematurely discontinue the study should complete an EDV and have their BRV dose down titrated by a maximum of half the dose every week for a maximum of 4 weeks until a dose of 1mg/kg/day (50mg/day for subjects with body weights >50kg) is reached.	All subjects who prematurely discontinue the study should complete an EDV and have their BRV dose down titrated by a maximum of half the dose every week for a maximum of 4 weeks until a dose of 1mg/kg/day (50mg/day for subjects with body weights >50kg) is reached. Equally, all subjects completing the study but switching to treatment	To add down-titration information for subjects who do not continue BRV treatment after completing the study

Section impacted	Key components of previous text	Key components of amended text	Rationale
		other than BRV should have their BRV dose down titrated.	

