Section 7.2.4	Not applicable.	
Section 7.2.4 Alternative study treatment supply due to COVID-19
 
When a subject can no longer return to the study site but will continue in the study, the following methods may be used to provide study treatment:
 
• Site to subject: In instances where site staff can ship study treatment dispensed from the site or pharmacy supply directly to the subject, or• Depot to subject: In instances where it is not possible for the site staff to access study treatment and/or ship study treatment dispensed from the site or pharmacy supply directly to the subject.	To mitigate risk related to COVID-19
Section 7.7	The IMP (oral solution or oral tablets) will be supplied to the subject/parent(s)/legal representative(s) at the TV(s) (directly enrolled subjects only), EV, MEV, FEV, YEV, and at the EDV in the case of early discontinuation.	The IMP (oral solution or oral tablets) will be supplied to the subject/parent(s)/legal representative(s) at the TV(s) (directly enrolled subjects only), EV, MEV, FEV, YEV, and at the EDV in the case of early discontinuation. The IMP for down-titration will be dispensed at the FV for subjects who complete the study but do not continue BRV treatment.	To add down-titration information for subjects who do not continue BRV treatment after completing the study
Section 8.11	Not applicable.	
• Appointment for the next visit should be scheduled for the end of the 4-week Down-Titration Period (maximum) if BRV treatment is not continued after study completion (FV), and study drug for down-titration should be dispensed	To add down-titration information for subjects who do not continue BRV treatment after completing the study

Section impacted	Key components of previous text	Key components of amended text	Rationale
Section 9.1.2.1	Not applicable.	Occurrence of COVID-19 in subjects should be reported as either “suspected COVID-19” or “confirmed COVID-19.” For subjects where COVID-19 is still suspected despite a negative viral test, please report as “suspected COVID-19.”	To document adverse events of suspected or confirmed COVID-19

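### Completers who taper off brivaracetam from the Final Visit cannot meet the last visible trigger for repeat ECG, laboratory and phenytoin tests at the Safety Visit

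*Protocol*

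**What the plan says.** Amendment 8 (Section 16.8) creates the new route. Its entry for Section 5.1 starts the dose reduction after the EDV, "or following the FV for subjects who complete the study but do not continue BRV treatment, subjects will have their BRV dose reduced" stepwise. Its entry for Section 7.2.3 puts the two groups on the same footing: "Equally, all subjects completing the study but switching to treatment" other than BRV should also be tapered. Section 7.7 and Table 5-2 footnote g provide for dispensing taper drug at the FV. Section 8.11 adds the follow-up booking: "Appointment for the next visit should be scheduled for the end of the 4-week Down-Titration Period (maximum) if BRV treatment is not continued".

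The SV rules are older. Section 8.10, as last set out in Amendment 4 (Section 16.4, Change #37), lists "Laboratory assessments for safety (to be performed only if abnormal at the EDV". The Amendment 4 schedule reprinted in Section 16.5 carries footnote f on the SV column: "At the SV, ECGs, laboratory assessments for safety, and determination of phenytoin plasma concentration will be performed only if abnormal at the EDV".

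Section 9 once held matching sentences: "An ECG will be performed at the SV only if the ECG results at the EDV are abnormal" and, for phenytoin, "Blood samples will only be collected at the SV if the plasma levels of phenytoin are abnormal at the EDV". Amendment 5 took both out, giving as its reason: "Remove information provided in Section 5.2 to decrease redundancy". The schedule was thus meant to carry the rule from then on.

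**The concern.** The EDV belongs to subjects who stop prematurely, and the FV to those who stay until the study ends. A rule conditioned on the EDV result cannot be met by a completer, however abnormal the FV result. Before Amendment 8 the last listed text gave completers no taper, so the wording did no harm. Amendment 8 gave some completers a taper of up to 4 weeks and a follow-up visit, but no listed change carries the trigger across.

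At stake is follow-up of individual children in a study whose primary objective is long-term safety. Two children may stop the same drug with the same abnormal ECG or haematology result, and only the early discontinuer has an off-drug repeat in the schedule.

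**Working it through.** No figure is involved, so the check sets the texts side by side.

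**1. Who has which visit.** Amendment 8's Section 7.2.3 assigns the EDV to premature discontinuers. The change list for Section 8.11 (Change #47, made with Amendment 3) and Section 1 as amended by Amendment 5 assign the FV to subjects who continue to the end.

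**2. What the last visible schedule marks** (Amendment 4 Table 5-1, reprinted in Section 16.5):

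| Test | FV | EDV | Down-Titration Visit (DTV) | SV |
|---|---|---|---|---|
| ECG | yes | yes | no | conditional (footnote f) |
| Safety laboratory | yes | yes | no | conditional (footnote f) |
| Phenytoin, if applicable | yes | yes | no | conditional (footnote f) |

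None of the three is done at the DTV, so the SV is the only scheduled place for a repeat. Physical and neurological examinations, psychiatric and mental status, vital signs, C-SSRS and adverse event recording are marked at the SV without the condition.

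**3. Whether footnote f survived Amendment 5.** Footnote f was deleted from the new Table 5-1, which covers only the Entry Visit. For the new Table 5-2, only footnote a is listed as removed, with the rest relettered. The letters can be counted:
- EEG was g, the 7th; with a gone it is 6th, f. Amendment 5 prints f, and Amendment 6 still does.
- FV dispensing was h, the 8th; it becomes 7th, g. Amendment 8 prints g.
- j (10th), m (13th) and n (14th) become i, l and m, as printed.
- q (17th) drops to 16th, and the added footnote p pushes it back to q, as printed.

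Had the SV trigger also been dropped, EEG would be e and dispensing f. The lettering therefore leaves a footnote at e, where the SV trigger belongs.

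**4. Whether later lists change the trigger.**
- Amendment 5's entry for Section 8.10 covers head circumference, urinalysis and the pregnancy test.
- Amendment 6's Table 5-2 changes cover footnotes f, m and q, and it has no entry for Section 8.10.
- Amendment 7 touches only Section 9.1.4.
- Amendment 8 goes from Section 7.7 to 8.11 to 9.1.2.1, with footnote g its only Table 5-2 entry.

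**5. Related text.** As last listed in Amendment 5, Sections 1 and 9 describe the Down-Titration and Safety Periods for premature discontinuers only. Amendment 8's Section 1 entries deal with maximum dose and duration of participation.

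**6. Applied to a completer who stops BRV.** The path is FV, taper, a visit at its end, and then, through the next-visit bullet that Amendment 5 added to Section 8.9, plausibly the SV. There the condition refers to a visit that did not take place. For abnormal hepatic values the gap is closed by Section 9.2.2, which requires a repeat. For ECG, the remaining laboratory tests and phenytoin, nothing visible closes it.

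**The case against.** The strongest reply is that texts of different ages are being compared. The trigger is visible only in Amendment 4 wording, the taper is Amendment 8 wording, and the current Section 8.10 and Table 5-2 lie in the part of the protocol that was not available. The logs from Amendment 5 on list key components of changes, and Amendments 5 and 6 say that minor editorial changes are left out. They can also miss footnote changes: the Bayley-III footnote of Table 5-1 is j in Amendment 5 and k after Amendment 6, with no added footnote listed. A footnote letter shows position, not wording. All of this stands, so the point is an inference to be confirmed. It does not treat superseded text as current; it asks whether a rule was changed when a new route was added, and no listed change does so.

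Second, no visible text says outright that tapered completers attend an SV. That also stands. A reader might infer that the protocol contradicts itself about the SV, or denies these children drug-free follow-up. The documents do not support either: the FV booking and the Section 8.9 bullet plausibly lead to the SV, and Amendment 8 treats the two groups alike for tapering. What is missing is an explicit statement.

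Third, much is covered already. Abnormal hepatic values are repeated, liver events are followed until they normalise, stabilise or return to baseline, unscheduled visits exist, and an investigator may repeat any test on clinical grounds. This limits the point to the other tests.

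**Conclusion.** The point holds as a minor gap in alignment. On the last visible rules, a completer who stops BRV with an abnormal FV ECG, non-hepatic laboratory or phenytoin result has no scheduled off-drug repeat.

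The conclusion rests on two assumptions: that the EDV-only trigger still stands in Section 8.10 and as Table 5-2 footnote e, and that these completers are meant to reach the SV. If the second fails, changing the trigger alone would not help, which is why the fix also states the visit sequence.

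The number of children affected is not given and cannot be derived. It is probably small, because approval, a managed access programme and transfer to another BRV study all lead to continued BRV. A reader might go on to infer a bias in the primary variables. The documents do not support that: those variables are treatment-emergent adverse events and serious adverse events, and adverse event recording at the DTV and SV does not depend on the EDV result.

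**What to change.** First confirm the current wording of Section 8.10 and the Table 5-2 SV footnote. If the trigger still names only the EDV:

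1. In both places, make the condition: abnormal at the EDV or, for completers who stop BRV, at the FV.
2. In Section 8.11, state that completers who taper off BRV attend the DTV and, after the 2-week drug-free period, the SV. Align Sections 1 and 9 with this.

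The cost is a few words in four sections and one footnote, plus a small number of repeat ECGs or samples, done only after an abnormal FV result.
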